### **9.8 Serious Adverse Event Follow-up**

All SAEs will be followed until the end of study or resolution, unless related to study drug and continuing or reported after the end of the study, in which the related SAE will be followed until any of the following occur (whichever comes first):

- The event resolves.
- The event has stabilized.
- The event returns to baseline, if a baseline value is available.
- It is unlikely that any additional information can be obtained (e.g., subject or health care practitioner refuses to provide additional information; lost to follow-up after demonstration of due diligence with follow-up efforts).
- Further follow-up is not warranted based upon the medical judgment of the investigator.
- Death

All ongoing and new SAEs with a start date within 30 days of last dose of study drug and assessed as "Unrelated" to study drug will be followed until resolution or until  $30 \pm 7$  days after last dose of study drug administration, whichever is earlier.

### **9.9 Expedited Reporting of SAEs**

A SUSAR is a SAE that is considered "unexpected" and assessed as related to the study drug by the Investigator or the Sponsor. All SAEs deemed related to the study drug and not expected based on the most current IB are subject to expedited reporting by the Sponsor to the applicable Regulatory Authorities. Therefore, the investigator or study site personnel must report all SAEs

to Nektar Therapeutics Drug Safety or its designee within **24 hours** of first becoming aware of the event.

Fatal or life-threatening SUSARs will be reported by the Sponsor to the Regulatory Authorities as soon as possible, but no later than 7 calendar days after Sponsor or Sponsor's designee has first knowledge of the minimum criteria for expedited reporting. Non-fatal or non-life-threatening SUSARs will be reported to the Regulatory Authorities, IRBs/IECs, and Investigators as soon as possible, but no later than 15 calendar days after Sponsor or Sponsor's designee has first knowledge of the SUSAR.

Reporting of SUSARs to all applicable Regulatory Authorities will be done by Nektar Therapeutics Drug Safety or designee as per local country and regional regulations.

Notification of SUSARs to the central IRBs will be done by Nektar Therapeutics Clinical Operations or designee in accordance with the SOPs and policies of the IRBs. Reporting to local IRBs will be done by the applicable study site personnel as per their institutional guidelines. Adequate documentation must be provided to Nektar Therapeutics Clinical Operations or designee, showing that the local IRB was properly notified.

#### **9.10 Ongoing Safety Monitoring**

Subject safety will be assessed throughout the study by a Safety Review Committee consisting of at minimum the Medical Monitor, Sponsor Clinical Lead and Sponsor Pharmacovigilance Lead or designee by review of SAEs.

## 10.0 EFFICACY EVALUATIONS

Due to the nature of this study, no specific schedule or type of tumor measurements/assessments are dictated within the protocol. These will be conducted as per the local standard of care until disease progression. Data on best response and disease progression (per physician assessment) will be collected according to RECIST criteria version 1.1 ([Eisenhauer et. al., 2009](#)).

Radiographs that document response, stable disease, or progression should be performed according to routine patterns of care and (preferably original) copies should be maintained by the Investigator for review by the Sponsor, if requested.

Approximately every 12 weeks ( $\pm 4$  weeks) following the End-of-Treatment visit, subjects will have their medical records reviewed and may be contacted to assess disease status, survival status, receipt of subsequent anti-cancer therapy, and resolution of all toxicity attributable to study drug. Disease status during follow-up will only be assessed if the subject has not demonstrated disease progression since receiving NKTR-102. Quarterly follow-up will continue until death, withdrawal of consent by subject, physician decision, lost to follow-up, or the study is terminated by the Sponsor.

## 11.0 QUALITY CONTROL AND QUALITY ASSURANCE

Nektar Therapeutics shall implement and maintain quality control and quality assurance procedures with written standard operating procedures to ensure that the study is conducted and data are generated, documented, and reported in compliance with the protocol, GCP, and applicable regulatory requirements.

All protocol deviations and the reasons for such deviations are to be documented in the source documents and reported to Nektar Therapeutics.

### 11.1 Changes to the Protocol

The Investigator may not deviate from the protocol without a formal protocol amendment having been established and approved by an appropriate IRB/IEC, except when necessary to eliminate immediate hazards to the subject. Any deviation may result in the subject having to be withdrawn from the study and rendering that subject non-evaluable.

### 11.2 Monitoring

In accordance with 21 CFR § 312.56, ICH GCP and local regulations, the clinical monitor will periodically inspect all study documents, research facilities, and clinical laboratory facilities associated with this study at mutually convenient times during and after completion of the study. As required by 21 CFR § 312 Subpart D, ICH GCP and local regulations: Responsibilities of Sponsors and Investigators, the monitoring visits provide the Sponsor with the opportunity to evaluate the progress of the study; verify the accuracy and completeness of submitted data; ensure that all protocol requirements, applicable FDA, ICH GCP and local regulations, and Investigator's obligations are being fulfilled; and resolve any inconsistencies in the study records. This includes inspection of all documents and records that are required to be maintained by the Investigator, including but not limited to medical records (office, clinic, or hospital) for the subjects in this trial. The names and identities of all research subjects will be kept in strict confidence and will not appear in the CRFs or other records provided to or retained by the Sponsor. The IND regulations also require the Investigator to allow authorized representatives of the FDA and European Union Regulatory Authorities to inspect and make copies of the same records. The names and identities of the subjects need not be divulged to the Sponsor; however, the records must nevertheless be inspected. This can be accomplished by blacking out the subject's name and replacing the name with the subject's study identification number. If these requirements are in conflict with local regulatory restrictions or institutional requirements, the Investigator must inform the Sponsor of these restrictions prior to initiation of the study.

## 12.0 STATISTICAL CONSIDERATIONS

### 12.1 Analysis Populations

**Safety Population:** The safety population consists of all subjects who receive NKTR-102 for Injection. Unless otherwise stated, all safety analyses will be based on this population.

### 12.2 Endpoints and Planned Analyses

The primary endpoint of this study is assessment of safety for subjects receiving continued NKTR-102 therapy.

The MedDRA medical dictionary will be used to map the AE/SAE verbatim terms to specific system organ classes and preferred terms. The incidence and duration of AEs will be tabulated by MedDRA preferred term, system organ class, severity and relationship to study drug. The maximum intensity and frequency of AEs will be summarized by treatment (dose level). By-subject listings will be provided. No formal statistical testing is planned for AE or other safety and tolerability data.

Tumor response will be summarized by histological tumor type and tabulated using by-subject listings based on disease assessments from this protocol.

Other data will be tabulated using by-subject listings.

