## **2.2 Study Rationale**

This study is designed to allow an extension period of NKTR-102 therapy for subjects who previously received NKTR-102 during a clinical study and are without signs of disease progression since receiving NKTR-102.

The estimated study duration is approximately 5 years. The duration of treatment in this study is estimated to be approximately 2 years. Subjects may continue to receive repeated cycles of study drug treatment until progression of disease, unacceptable toxicity, death, withdrawal by subject, Investigator decision, lost to follow-up, or study is terminated by the Sponsor. Since this trial may involve the longest exposure to NKTR-102 to date, it will allow for the collection of safety data, particularly serious adverse events (SAEs) that may appear only after long-term exposure to NKTR-102.

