6.0 STATISTICAL CONSIDERATIONS

6.1 General Considerations

Summary statistics for continuous variables will include the mean, standard deviation, median, and range (minimum and maximum). The mean and median will be presented to one decimal place beyond which the data were captured. The standard deviation will be presented to two decimal places beyond which the data were captured. The minimum and maximum will be presented to the precision with which the data were captured.

Categorical variables will be presented as frequency counts and percentages. A row or column denoted 'Missing' will be included in count tabulations where necessary to account for dropouts and missing values. Percentages will be rounded to 1 decimal place and the percent will be suppressed when the count is zero. The denominator will be the number of patients in that dose schedule within the population of interest unless otherwise noted.

All analyses will be summarized for all patients (Total) and by dose level if sample size allows. Data listings will be created to support each table and to present all data. Data listings will be presented by subject number (combination of original NKTR-102 study ID, subject and site ID).

Neither hypothesis testing nor a specific sample size is required for this study.

We will use the term "Original NKTR-102" when referencing the study where a subject first exposed to NKTR102 before rolling over to current study, "Current" to indicate 11-PIR-09 (extension) study and "Overall" to indicate information inclusive of the original NKTR-102 and current throughout this document. The default implication is "Current", when no study specific information is specified,.

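### AE tables give only patient percentages although time on drug is open-ended, so they count late events without showing their timing or their rate among subjects still exposed

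*Protocol*

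**What the plan says.** **AE analysis.** Protocol 12.2 makes safety during continued treatment the primary endpoint, although the primary objective in 3.1 is access to the drug. For the main tables it states: "The incidence and duration of AEs will be tabulated by MedDRA preferred term, system organ class, severity and relationship to study drug". For the split by dose it states: "The maximum intensity and frequency of AEs will be summarized by treatment (dose level"). It adds by-subject listings and plans no formal test of safety data. It names no person-time or per-cycle rate and no onset interval.

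**Form of the tables.** SAP 6.1 supplies it: "Categorical variables will be presented as frequency counts and percentages". On the denominator: "The denominator will be the number of patients in that dose schedule within the population of interest unless otherwise noted". On the split: "All analyses will be summarized for all patients (Total) and by dose level if sample size allows". All subjects are treated every 21 days, so I read dose schedule here as dose group.

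**Time on drug.** Protocol 2.2 estimates about 2 years of treatment but sets no end: "Subjects may continue to receive repeated cycles of study drug treatment until progression of disease, unacceptable toxicity, death, withdrawal by subject, Investigator decision", with loss to follow-up and sponsor termination as the remaining reasons. The same section expects possibly the longest exposure so far and names as the particular interest "serious adverse events (SAEs) that may appear only after long-term exposure to NKTR-102".

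**Related data.** AE start and stop dates are collected (Protocol 9.2). SAP 6.3 derives study day since first dose of the original study. SAP 7.5 summarises overall duration, cycles and cumulative dose, but apart from the AEs. The SAP text available ends at 7.6 (Efficacy Analysis) and contains neither an AE section nor the table shells listed as Attachment 1.

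**The concern.** A percentage of patients ignores how long each was observed. With open-ended treatment, one subject may contribute a single cycle and another two years of cycles, yet each adds one to the denominator. Two things are then lost.

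First, a risk that begins only after long exposure is diluted by subjects who stopped before it could begin, and the table does not say how many were still exposed. That is the question Protocol 2.2 raises.

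Second, percentages by dose level combine the risk per cycle with the number of cycles received. Dose is not randomised (Protocol 4.4). A lower dose may reflect earlier toxicity or hepatic impairment (6.5), and toxicity leads to further reductions (6.7). The text does not say whether an AE counts under the entry dose or the dose at onset.

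At stake is whether the primary-endpoint tables can describe long-term toxicity without a reader rebuilding it from listings.

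**Working it through.** **1. Inputs.** The plan has no figure to reproduce: SAP 6.1 requires neither a hypothesis test nor a sample size. From the documents:
- 21-day cycles, about 2 years of treatment, and up to 150 subjects (Protocol synopsis).
- Onset in the Phase 3 study: Grade 3 diarrhea at a median of 43 days, range 3 to 488 (Protocol 2.1.2.4); Grade 3 or higher neutropenia at a median of 120 days (2.1.2.5).
- Median PFS of 4.7 months in the Phase 2 breast study (2.1.2.2), used only as one scenario for time on drug.

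All risks, and the distribution of time on drug, are my assumptions.

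**2. Does timing matter for this drug?** With cycles starting on days 1, 22, 43, 64, 85 and 106, day 120 falls in the sixth cycle. The sponsor's own data therefore show important toxicity well after the first dose.

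**3. Same risk, different number of cycles.** With constant risk p per cycle, the expected percentage with at least one event after k cycles is 1 − (1 − p)^k. Two years is 2 × 365.25 / 21 = 34.8, about 35 cycles. Example: 1 − 0.98^4 = 1 − 0.9224 = 7.8%.

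| p per cycle | 4 cycles | 8 cycles | 16 cycles | 35 cycles |
|---|---|---|---|---|
| 1% | 3.9% | 7.7% | 14.9% | 29.7% |
| 2% | 7.8% | 14.9% | 27.6% | 50.7% |
| 3% | 11.5% | 21.6% | 38.6% | 65.6% |

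Risk per cycle is identical along each row; only time on drug changes.

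**4. Same data per cycle.** Expected cycles at risk up to the first event are [1 − (1 − p)^k] / p. At p = 2% this is 0.0776 / 0.02 = 3.88 cycles for k = 4 and 0.2762 / 0.02 = 13.81 for k = 16. Events divided by cycles give 0.0776 / 3.88 = 0.2762 / 13.81 = 2 per 100 cycles in both.

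**5. A late-onset risk.** Assume no risk before month 12, then 0.20 per patient-year, with exponential time on drug at rate μ = ln 2 / median (in years). The share reaching month 12 is exp(−μ). Of those, 0.20 / (0.20 + μ) have the event on drug. The crude percentage is the product. With a median of 4.7 months, μ = 1.770, exp(−μ) = 0.170, and 0.20 / 1.970 = 10.2%.

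| Median time on drug | Reaching month 12, of 150 | Crude percentage | Among those reaching month 12 |
|---|---|---|---|
| 4.7 months | about 26 | 1.7% | 10.2% |
| 12 months | 75 | 11.2% | 22.4% |
| 24 months | about 106 | 25.9% | 36.6% |

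The rate after month 12 is 0.20 per patient-year in every row, while the crude figure runs from 1.7% to 25.9%.

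**The case against.** **The SAP safety section is not visible.** The denominator in SAP 6.1 is a general rule that allows exceptions, and 6.3 derives study days from the original study that Sections 7.1 to 7.6 do not name. The missing section or shells may use them. This stands: it cannot be said that the SAP lacks exposure-adjusted output. But Protocol 12.2 itself describes the primary-endpoint analysis without it. The SAP also cites protocol amendment 2.0 of 25 September 2013, while this protocol reports safety data as of May 2015.

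**Late toxicity is not invisible.** A reader might infer that the planned tables cannot show late-onset toxicity at all. The documents do not support that. A late SAE would be counted, its timing could be recovered from AE dates, listings and the derived study day, and a Safety Review Committee reviews SAEs (Protocol 9.10). What is missing is a summary of timing and of rate among the exposed.

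**No dose comparison is planned.** A reader might also infer that the tables will reverse a dose comparison. It is arithmetically possible: a hazard of 0.20 per year for 6 months gives 1 − exp(−0.10) = 9.5%, and half that hazard for 24 months gives 1 − exp(−0.20) = 18.1%. But nothing shows that exposure differs between dose groups, no test is planned, and the split itself depends on numbers.

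**Dose is only partly an outcome of tolerability.** Subjects from the hepatic-impairment study keep an assigned dose, and grouping by entry dose would not move subjects after a reduction. This stands; the remaining point is that the grouping rule is not given.

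**Conclusion.** The concern holds in a limited form. As described, AE incidence is a set of patient counts and percentages. They can record a late event but do not show its timing or its rate among subjects still exposed, and any by-dose percentages mix risk with time on drug. At an assumed 2% risk per cycle, 4 against 16 cycles gives 7.8% against 27.6%; over 1% to 3% the pairs run from 3.9% against 14.9% to 11.5% against 38.6%. These figures show how large the effect can be. They do not predict this study, whose risks and exposure by dose are not given.

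The analysis is descriptive, so no error rate or formal conclusion is affected. This is a worthwhile, inexpensive improvement to the primary-endpoint reporting, conditional for the SAP on what its safety section already contains.

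**What to change.** Keep the crude tables. Add two descriptive tables to Protocol 12.2, and to the SAP safety section if it does not already have them:

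1. **Per 100 treatment cycles in the extension:** new-onset Grade 3 or higher AEs and SAEs, in total and by last dose received before onset, with cycles at that dose as denominator. State whether all events or only the first per subject count; if only the first, stop counting cycles there.
2. **By interval since first dose of the original study** (for example 0–6, 6–12, 12–24 and over 24 months): the same events, with the number at risk in each interval. Subjects enter after earlier treatment, so count them as at risk only from their first extension dose. Early intervals may hold few subjects. State when risk ends; the AE collection window in Protocol 9.2 is a natural choice.

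Protocol 9.2 enters related AEs ongoing from the original study as new AEs marked as continuing, and allows the same for unrelated ones. Exclude these from both tables and show them separately; SAP 7.3.1 already summarises AEs ongoing at entry. Label by-dose rates as descriptive, because a per-cycle denominator does not remove non-random dose assignment.

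**Cost.** No new data are needed. SAP 6.3 defines total cycles, but not cycles at each dose or the last dose before AE onset, so both must be derived from dosing records and AE dates. This is modest extra programming.

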## **13.0 ETHICS**

This study will be conducted according to the provisions of the Declaration of Helsinki (October 2008) and in accordance with FDA regulations (21 CFR § 11, 50, 54, 56, and 312), with the ICH guidelines on GCP (ICH E6), as well as with any and all applicable federal, state and/or local laws and regulations.

### **13.1 IRB/IEC Approval**

Prior to enrollment of subjects into the study, as required by Federal regulations (21 CFR § 56), ICH E6 GCP and local regulations, the protocol and informed consent form will be reviewed and approved by an appropriate IRB or IEC. By signing the Statement of Investigator Form FDA 1572, the Investigator assures that all aspects of the institutional review will be conducted in accordance with current federal regulations. A letter documenting the IRB or IEC approval with the names and titles of the IRB or IEC members must be received by the Sponsor prior to the initiation of the study. Amendments to the protocol will be subject to the same requirements as the original version of the protocol.

The Investigator, the Sponsor or designee will submit a progress report at least once yearly to the IRB or IEC and Regulatory Authorities. The frequency of these reports will depend on local regulations. As soon as possible after completion or termination of the study, the Investigator will submit a final report to the IRB or IEC and to the Sponsor. The results should be reported per the IRB or IEC's local requirements.

The Investigator, the Sponsor or designee is required to notify the IRB or IEC of SAEs, or any other information that may affect the safe use of the study drug during the course of the trial, per the IRB or IEC's local requirements.

### **13.2 Written Informed Consent**

Written informed consent must be obtained from each subject or subject's legal representative before entering the study. Subjects/legal representatives will be informed of the nature of the study, and the ICF must be presented to each subject/subject's legal representative in the language in which the subject/subject's legal representative is fluent. By signing the Statement of Investigator Form FDA 1572, the Investigator ensures that informed consent will be obtained from each subject/legal representative prior to any protocol-specific procedures, and that informed consent will be obtained and documented in accordance with current state and federal regulations. Signed and dated ICFs will be retained by the Investigator with the study records. Each subject/legal representative will be given a copy of the signed and dated consent form.

## **14.0 DATA HANDLING AND RECORD KEEPING**

### **14.1 Case Report Forms and Source Documents**

#### **14.1.1 Study Records**

During the study, the Investigator will maintain adequate records for the study, including medical records, records detailing the progress of the study for each subject, laboratory reports, CRFs, signed informed consent forms, drug disposition records, correspondence with the IRB or IEC and regulatory agencies AE reports, and information regarding subject discontinuation and completion of the study.

#### **14.1.2 Case Report Forms**

Case report forms will be used in this study. These forms are used to transmit the information collected in the performance of this study to the Sponsor or Sponsor's designee and Regulatory Authorities. Case Report Forms must be completed in English. The Investigator must review the CRFs for completeness and accuracy and must approve the appropriate CRF as indicated. Furthermore, the Investigator retains full responsibility for the adequacy and accuracy of all data entered on the CRFs.

### **14.2 Retention of Essential Documents**

All records and documents pertaining to the study including, but not limited to, those outlined above (see Section 14.1.1) will be maintained by the Investigator for a period of at least 2 years after FDA/European Medicines Agency (EMA) approval of the drug or at least 2 years after withdrawal of the IND under which this study was conducted, whichever is longer. In countries outside the US, as a minimum, records must be kept for the period of time required by the US FDA, and should also comply with the local country regulatory requirements, if longer retention times are required than in the US. In order to avoid any possible errors, the Investigator will contact the Sponsor before transferring or destroying any study records. The Investigator will also promptly notify the Sponsor in the event of accidental loss or destruction of any study records.

